Meeting recommendations are drafted by the ES and are distributed for review by the DSMB Chairperson within two working days after the meeting. Once the recommendations are accepted by the Chairperson, the ES sends the recommendations to the full DSMB. Comments from DSMB members are obtained within two working days. Once finalized, the recommendations are circulated to the DSMB and the Sponsor-Investigator for their review. The Sponsor-Investigator has 14 calendar days to submit a formal, written response to the recommendations. If the DSMB has any further questions or concerns, the ES will notify the Sponsor-Investigator for further clarification via email. It is the responsibility of the Sponsor-Investigator to distribute this report to all co-investigators and to assure copies are submitted to all the IRBs associated with the study. The response will also be discussed at the following DSMB meeting.

Meeting Minutes

The full meeting minutes are drafted by the ES and distributed for review and approval by the Chairperson within 5 business days after the meeting. Any recommendations are inserted at the end of the minutes. Once approved by the Chairperson, the ES sends the minutes to the full DSMB. Comments from DSMB members are generally obtained within 5 working days after the meeting and meeting minutes finalized no later than 30 calendar days after the meeting. Each report concludes with a recommendation to continue, place on hold or to terminate the study. A formal vote to approve the minutes is held at the next DSMB meeting.

Additional Reporting

Status Reports (during active enrollment)

All clinical trials must provide semi-annual enrollment reports once the first participant is enrolled into the study. These reports will contain an Actual versus Expected graph and a CONSORT diagram and should be submitted to the Sponsor-Investigator through the ES. The reports will be shared with the DSMB for their reference.

Unanticipated Problems

Unanticipated problems are 1) unexpected events that are 2) related or possibly related to participation in the research that 3) place participants or others at greater risk of harm than was previously known or recognized. All three criteria above must be met to qualify the event as an unanticipated problem. The Office for Human Research Protections (OHRP), the Department of Health and Human Services (HHS), provides a complete definition and the following guidance for reporting unanticipated problems to the IRBs: *Guidance on Reviewing and Reporting Unanticipated Problems Involving Risks to Participants or Others and Adverse Events*. (http://www.hhs.gov/ohrp/policy/advevntguid.html). Unanticipated problems must be reported within 48 hours of the PI receiving notification of the event. The DSMB Chairperson reviews the unanticipated problems to determine if further action is required.

Serious Adverse Events

All Serious Adverse Events (SAEs) (regardless of expectedness, relatedness, or if they meet the definition for unanticipated problems) must be reported to the DSMB Chairperson within 48 hours of the Sponsor-Investigator receiving notification of the event. The report will include a description of the event, as well as the Investigator's assessment of expectedness, relatedness, and other information, as relevant. Any action taken by the investigative team should be provided in the report. The DSMB Chairperson will be provided with this information but will provide an independent assessment on attribution and expectedness, as well as whether further action is recommended (e.g. collection of follow up information).

Discrepancies with Assessments Concerning Unanticipated Problems

On occasion, there may be disagreements between the Sponsor-Investigator and the DSMB regarding the assessment and/ or management of an event that qualifies as an unanticipated problem. The following excerpt gives guidance for cases where there is a difference of opinion among the DSMB (referred to as the "monitoring entity" in the excerpt below) and the investigator http://www.hhs.gov/ohrp/policy/advevntguid.html.

If the investigator determines that an adverse event is not an unanticipated problem, but the monitoring entity subsequently determines that the adverse event does in fact represent an unanticipated problem (for example, due to an unexpectedly higher frequency of the event), the

monitoring entity should report this determination to the investigator, and such reports must be promptly submitted by the investigator to the IRB (45 CFR 46.103(b)(5)).

Please note: The DSMB and the Sponsor-Investigator may have iterative discussions regarding the assessment and may later come to agreement regarding the assessment and/or management of an AE. In cases where the DSMB and Investigator come to an agreement after discussions and the event is determined not to be an unanticipated problem, the Investigator is not required to report the event as an unanticipated problem to the IRB. Such discussions should take place promptly so as not to delay appropriate reporting to the IRB.

Please also note that additional reporting requirements [e.g., to the Food and Drug Administration (FDA) and the IRB] are the responsibility of the Sponsor-Investigator.

Protocol Deviation/Violations

Protocol deviations/violations that impact participant safety should be reported to the DSMB Chairperson (through the ES) within 48 hours of the Sponsor-Investigator becoming aware of the event. Protocol deviations/violations that occur but do not affect participant safety are submitted with the routine DSMB meeting report. The Investigator must also adhere to the Institution's policy on reporting protocol deviations/violations to the IRB.

Additional reporting may be required if the violation meets the definition of an unanticipated problem as described in the OHRP, HHS guidance (http://www.hhs.gov/ohrp/policy/advevntguid.html).

Protocol Amendments

Requests for protocol amendment approvals must be submitted by the Sponsor-Investigator for review by the DSMB between regularly scheduled meetings. Approvals may be conducted via email correspondence, deferred until the next regularly scheduled meeting, or a call may be scheduled if immediate discussion is warranted. The Sponsor-Investigator is notified by the ES of the approved changes. IRB review of protocol amendments are separate from this process and are the Sponsor-Investigator's / site-investigator's responsibility.

Communication with the DSMB

To maintain the independent nature of the DSMB, the Sponsor-Investigator and study staff should only communicate DSMB-related requests, questions, or concerns through the ES. The DSMB members should only communicate with the Sponsor-Investigator through the ES.

Release of Study Data

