complete reports on data stored in REDCap. This entails export to our local secure drive, imports as SAS datasets, and production of multiple types of output for data management and reporting. Reports, overall and site-specific, will be provided for data management (e.g., flagging of questionable or missing data and missing forms, variable description, flagging of overdue visits) and for investigators (e.g., screening and enrollment, follow-up tracking, exits).

Microsoft OneDrive will be used as a central repository to store all nasal endoscopy and CT files collected during the course of the study. This HIPPA compliant database will provide access for our central reader while maintaining a backup of study files should additional review be required. All data will be stored with study identification numbers.

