The Executive Secretary (ES) drafts meeting agendas in consultation with the Sponsor-Investigator, DSMB Chairperson, and program staff. The agenda is sent to the full DSMB and the Sponsor-Investigator for input. The ES coordinates the DSMB meetings and conference calls and provides logistics support and meeting summaries. The ES will transcribe the meeting recommendations and minutes and will distribute them to the Sponsor-Investigator, DSMB Chairperson and members. The ES is the primary contact point for DSMB communication with the Sponsor-Investigator.

[name] has been appointed as the DSMB Executive Secretary.

CONFLICT OF INTEREST

Individuals invited to serve on the DSMB as must disclose any potential conflicts of interest, whether real or perceived, to the Sponsor-Investigator. Conflicts of interest can include, but are not limited to, professional, proprietary, and miscellaneous interests. Any real or potential conflicts that develop during a member's tenure on a DSMB must be disclosed for the Sponsor-Investigator consideration at the time the potential conflict is realized. In addition, written documentation attesting to an absence of conflict of interest is required annually.

Confidentiality

Each member of the DSMB must sign a statement of confidentiality annually. All materials, discussions, and proceedings of the DSMB are completely confidential. Members and other participants in DSMB meetings are expected to maintain confidentiality.

BOARD PROCESSES

Prior to commencement of recruitment, the study team drafts or revises study materials (protocol, DSMP and report templates, and any other materials required for the DSMB's review). The study team delivers relevant materials to the ES, who facilitates the review process with the DSMB.

- a) Upon completion of the initial review, the DSMB members are to send the ES their comments for consideration. Accepted comments and recommendations are sent to the Sponsor-Investigator for review.
- b) ES concurrently schedules an introductory teleconference between the Sponsor-Investigator and DSMB. All discussions are confidential.

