The first meeting is held either by teleconference or in-person before initiation of the study to discuss the materials and whether the study is ready to commence, establish guidelines for monitoring and determine the format for future meetings. The Sponsor-Investigator and ES prepare the agenda to 1) review the study materials, 2) appoint the DSMB Chairperson and Safety Officer, 3) discuss the plan and timing for safety monitoring 4) make recommendations to initiate the study and/or modify the study materials and 5) review the charter. During the initial DSMB meeting, a representative provides a training session outlining the board process and DSMB procedures for all meeting participants (DSMB members, study staff and coordinator).

Version: 3.7.3 2Apr2024

Reports for both the open and closed sessions should be established at the initial DSMB meeting,

Page 47 of 58 IRB Form BIO 03152021 although changes throughout the study may be requested by the DSMB. In addition, the DSMB members will vote to recommend commencement of the study.

Routine meetings of the DSMB are held two times a year via video conference call. Attendance at all meetings is highly critical for all DSMB members. Each DSMB member is specifically selected for his/her expertise and thus the member's consistent participation ensures rigorous monitoring throughout the course of the study. The DSMB coordinator also attends all DSMB meetings and meeting sessions to provide logistical support and transcribe meeting summaries. Meetings are to be closed to the public because of participant confidentiality considerations.

All DSMB discussions are confidential. An ad hoc meeting of the DSMB may be called at any time by the Chairperson should ethical or patient safety issues arise. The suggestion to convene an ad-hoc meeting should be transmitted to the ES, who will notify the Sponsor-Investigator and DSMB coordinator. Depending on the situation, this meeting may include the Chairperson alone, a quorum of the DSMB, or the full DSMB.

Meeting Format

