DSMB meetings consist of open and closed sessions. Discussion held in all sessions is confidential. All invited meeting participants, including the investigators, institution staff and the ES, may attend **open sessions**. All sessions are normally attended by a minimum of three voting DSMB members. The Sponsor-Investigator and the study statistician must be present. The number of coordinating staff attending DSMB meetings should be minimized and only include experienced and trained staff. Other staff may be invited to attend only when appropriate. Open session discussion focuses on the conduct and progress of the study, including patient accrual, protocol compliance, and problems encountered. **Unmasked data are not presented in the open session.**

The closed session is normally attended by the DSMB members, the ES, and the unmasked study statistician or unmasked study team designee. If necessary, all unmasked safety data and efficacy data by treatment group may be presented during the closed session. The DSMB determines in advance, in what format it wishes to see the data during the closed session. The discussion during the closed session is completely confidential, and thus attendance is limited to the members listed in this section, based on their safety monitoring and oversight roles and responsibilities. The DSMB remains unmasked at all times during the closed session.

If necessary, an **open session** may be called following the closed session to clarify any questions that arise from the DSMB. A second **closed session** may also be held, if needed.

Ad-hoc meetings may be held at any time should ethical or safety issues arise. The suggestion to convene an ad-hoc meeting should be transmitted to the ES, who will notify the Chairperson.

Each meeting, whether routine or ad-hoc, must include a recommendation made by a formal DSMB majority to initiate, continue, place on hold or to terminate the study. The decision is ultimately made by the Sponsor-Investigator and sponsoring institution IRB, taking into consideration the recommendation of the DSMB. The vote may be postponed until further information is acquired. Should the DSMB decide to issue a termination recommendation, the full DSMB must vote. In the event of a mixed vote, majority vote will rule and a minority report will be appended.

Specific recommendations will be transmitted in writing to the Sponsor-Investigator within 7 days of meeting completion.

Meeting Materials

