DSMB report templates are prepared by the study staff, typically the statistician and/or the data coordinating center in consultation with the Sponsor-Investigator, to be reviewed by the DSMB members at the first meeting. Additions and modifications to the reports can be requested at any time throughout the study. The reports list and summarize safety data, as relevant, and describe the status of the study. All meeting materials must be sent to the ES at least two weeks prior to the meeting for distribution to the DSMB. The ES distributes study materials via the HIPPA compliant, central study data repository (Microsoft OneDrive, Redmond WA). Access will be limited to DSMB members and trained staff. Hard copies of the materials may be sent via express mail to DSMB members at their request. Materials are divided into two parts if requested: Part 1 contains open session materials, which may be shared with the study staff and meeting participants and referenced during any session of the meeting; and Part 2 contains closed session materials, which may contain sensitive or unmasked data and should be discussed in closed sessions only.

Part 1 – Open session materials include administrative reports by study site that describe patients screened, enrolled, completed, and discontinued, as well as baseline characteristics of the study population. Listings and summaries of adverse events and serious adverse events, along with any other information requested by the DSMB may also be in the open session report, but none of the data should be presented in an unmasked manner.

Part 2 – Closed session materials may contain safety data in aggregate, by masked treatment group (A/B presentation), by unmasked treatment group, or in other formats as requested by the DSMB. The closed session reports are confidential. Printed copies of the closed reports should be destroyed immediately following the meeting.

It is important that access to outcome data, when necessary, be limited to the study statistician and/or unmasked study team designee and the DSMB to protect the study from bias in patient entry and/or evaluation. Any unmasked study personnel should be pre-designated.

Meeting Recommendations

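### The DSMB charter's closed-session confidentiality rules conflict on who receives the minutes, who attends and who can open the files

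*Combined protocol and SAP*

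**What the plan says.** All of this is in Appendix C (DSMB charter) unless another section is named.

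- **Minutes, role description (DSMB Executive Secretary, ES).** "The ES will transcribe the meeting recommendations and minutes and will distribute them to the Sponsor-Investigator, DSMB Chairperson and members".
- **Minutes, procedure (Meeting Minutes).** A single set is described: "The full meeting minutes are drafted by the ES and distributed for review and approval by the Chairperson within 5 business days after the meeting". Circulation to the board follows: "Once approved by the Chairperson, the ES sends the minutes to the full DSMB". The Sponsor-Investigator is not mentioned at this step.
- **Closed session (Meeting Format).** Safety and efficacy data by unmasked arm may be shown where necessary. Those listed are the board, the ES and the unmasked statistician or another unmasked designee, and "attendance is limited to the members listed in this section, based on their safety monitoring and oversight roles and responsibilities".
- **Coordinator (Board Processes).** "The DSMB coordinator also attends all DSMB meetings and meeting sessions to provide logistical support and transcribe meeting summaries".
- **Files (Meeting Materials).** DSMB materials go out through the study's central OneDrive repository, and "Access will be limited to DSMB members and trained staff". The division into an open and a closed part is made only on request. The same section wants "access to outcome data, when necessary, be limited to the study statistician and/or unmasked study team designee and the DSMB".
- **Other use of OneDrive (Section 14.2).** It holds the endoscopy and CT files. "This HIPPA compliant database will provide access for our central reader while maintaining a backup of study files should additional review be required".

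**The concern.** A closed session works only if what is said and shown there stays with a defined group. Here the charter defines that group in one place and widens it in three others: the recipients of the minutes, the attendance of the coordinator, and access to the files.

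The minutes matter most. The Sponsor-Investigator has both sponsor and investigator duties and undertakes to conduct or supervise the study personally (Section 15.1). The charter's stated reason for restricting outcome data is to prevent bias in entering and evaluating patients. Sending closed-session content to that role would defeat this purpose, and a disclosure cannot be taken back.

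**Working it through.** The documents give no figure on this point, so there is none to reproduce and no arithmetic applies. The check sets the rules side by side.

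1. **Who gets the minutes.** The ES role description names the Sponsor-Investigator, the Chairperson and the members. The Meeting Minutes section names the Chairperson and then the full board. The two lists differ by exactly one recipient, the Sponsor-Investigator.

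2. **What the minutes contain.** The Meeting Minutes section describes a single, complete set. Neither it nor the role description asks for separate open and closed minutes or for redaction. The charter does protect printed closed reports, which are to be destroyed straight after the meeting. It has no equivalent rule for minutes.

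3. **Whether the Sponsor-Investigator may see closed content.** The closed-session list leaves the role out. The requirement that the Sponsor-Investigator be present stands in the paragraph on open sessions, and I read it as applying there. The outcome-data limit in Meeting Materials also leaves the role out. Points 1 to 3 together mean that following the ES sentence literally, with closed content in the minutes, would breach the outcome-data limit.

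4. **Coordinator.** Board Processes places this role at every session. The closed-session list in Meeting Format does not include it. The coordinator is not the ES under another title, because Board Processes has the ES notify the coordinator about ad hoc meetings. The two attendance rules cannot both be followed.

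5. **Files.** Two access rules stand in the same section. One covers board members and trained staff; the other, for outcome data, covers the statistician and/or unmasked designee and the board. Trained staff are not defined as unmasked, so the first rule is wider than the second. Because the open/closed division is optional, a meeting could have one undivided package under the wider rule. No separate restricted area is described.

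6. **Link to the central reader.** Section 14.2 gives the reader access to the OneDrive repository for imaging files. Meeting Materials uses the same platform for DSMB files but with its own access limit. No sentence gives the reader access to DSMB files. The finding here is a firewall that is not fully specified.

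**The case against.** The best defence is that the ES sentence is a one-line role summary, while the dedicated sections keep the two documents apart: recommendations go to the board and the Sponsor-Investigator, minutes to the board alone. That is a sensible reading and may be what was intended. But the charter does not say which section prevails, and the ES is the person who acts on both.

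Several further objections stand in part:

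- Nothing says that unmasked results are written into the minutes. All DSMB proceedings are declared confidential, and the board must see that the confidentiality plan is adequate. This makes the exposure conditional. A general duty of confidentiality still does not settle who the recipients are.
- Section 4.7 lists patients, treating physicians and local study personnel as blinded and does not name the Sponsor-Investigator. That is correct. The case for keeping closed results from this role rests on the charter's attendance list and its outcome-data limit.
- The closed list describes normal attendance, and the coordinator has only logistics and transcription duties. The consequence is therefore probably small, but the two rules still contradict each other.

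Four stronger readings are tempting, and the documents do not support them:

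- *The shared platform lets the central reader see DSMB reports.* A shared platform is not a shared folder, and Meeting Materials sets a separate access limit.
- *Exposure recurs at each of the twice-yearly meetings.* Unmasked data are shown only where necessary, and Section 14.9 plans no interim analysis.
- *Both co-primary outcomes are biased, with a calculable rise in type I error.* Aggregate arm results do not reveal any participant's allocation. Individual codes stay with the study data team (Section 4.7.1), and treating physicians are blinded. A physician who knew only arm-level results could not prescribe differently by arm. Under the null hypothesis there is also no true arm difference to leak.
- *Minutes are forwarded to all co-investigators.* The Sponsor-Investigator must pass on a report, but in context this is the recommendations.

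**Conclusion.** The concern holds as a conflict between stated rules. Who receives the minutes is contradictory, and open and closed content are not separated. Coordinator attendance is contradictory. File access is drawn wider than the charter's own limit on outcome data. This is more than missing detail, because following one sentence literally can break another.

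The consequence is conditional: arm-level results could reach the Sponsor-Investigator if unmasked data are shown, are then minuted, and the minutes are sent as the ES sentence says. The documents do not allow the probability of that sequence or the size of any bias to be quantified, and I give no figure. It should be corrected, with medium confidence. The text under the charter heading Release of Study Data was not available and may contain further rules. Any such rule would still have to be reconciled with the recipient list and the attendance rule discussed here.

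**What to change.** Amend Appendix C as follows:

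- **Minutes.** Keep separate open and closed minutes. Send the Sponsor-Investigator only the open minutes and the written recommendation. The ES holds the closed minutes until database lock. Use the same recipient list in the ES role description and in Meeting Minutes.
- **Materials.** Make the open/closed division mandatory.
- **Storage.** Keep closed files in a folder restricted to DSMB members, the ES and the pre-designated unmasked person. Remove the undefined trained staff from access to closed files.
- **Attendance.** Align the coordinator rule in Board Processes with the closed-session list in Meeting Format.

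The cost is charter wording and one folder permission. The charter states that it may be changed at any time. No visit, treatment or analysis is affected.
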